Human Research Protocol

Title: Randomized Trial of Text vs. Video Patient Educational Materials in Cirrhosis

PI: [name] MD

Version 0.5

Version Date: 10/7/2021

Background and Significance

Cirrhosis is a complex chronic disease, with several associated complications, numerous symptoms, and patients often require many medications. Cirrhosis is unfortunately linked to frequent hospitalizations and re-hospitalizations. Lack of medication compliance leads to hospitalizations, and increased disease understanding can improve medication compliance. Improved health literacy can prevent hospitalizations in other ways (preventing ED visits for ascites or HE). Based on internal QI data, we know that many patients with cirrhosis at U-M do not understand their medications and other aspects of their disease. Our essential purpose in this study is to compare the efficacy and patient satisfaction associated with traditional text cirrhosis education vs. recently-created educational videos on the same topics.

Specific Aims:

Aim 1: *Do educational materials improve patients' understanding of disease?*

Assess change in score for pre- and post-evaluations.

Aim 2: *Is one mode of patient education more effective than the other?*

Compare efficacy of educational materials when presented as text (Cirrhosis Toolkit) or video.

Aim 3: *Do patients prefer one mode of education over the other?*

Compare patients' preference for educational materials presented as text (Cirrhosis Toolkit) or video.

Aim 4: *How can these educational materials be improved?*

Collect feedback from patients on educational materials.

Research Design and Methods

Overview

We plan to enroll adult outpatients with cirrhosis who are evaluated at the University of Michigan Hepatology Clinic. We aim to enroll a maximum of 320 subjects with cirrhosis, into two main study arms. Arm 1 will include 160 responses from subjects who are newly diagnosed with cirrhosis, and Arm 2 will include 160 responses from subjects with history of cirrhosis.

After screening, and before being invited to respond to the study survey, participants will be randomized into one of 4 subgroups per each study arm, for a total of 8 possible subgroup assignments:

Arm 1: New Diagnosis		Arm 2: Previous Diagnosis	
1A: Cirrhosis Toolkit	1B: Cirrhosis Videos	2A: Cirrhosis Toolkit	2B: Cirrhosis Video
1A.1: General Cirrhosis Info	1B.3: General Cirrhosis Info	2A.1: General Cirrhosis Info	2B.3: General Cirrhosis Info

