1A.2: Ascites Info	1B.4: Ascites Info	2A.2: Ascites Info	2B.4: Ascites Info

Subgroups 1 and 2 will involve the presentation of educational materials in text-and-graphic format (Cirrhosis Toolkit), with each subgroup focusing on a single subject or section of the material. Subgroups 3 and 4 will be presented with similar material in video format, also focusing on a single subject per subgroup. Recruitment for this study will conclude once 40 subject-experiments have been completed for each subgroup.

Subjects will be given the option to be randomized into an additional study subgroup (For example: if they were randomized into subgroup 1A.1 in the first round, they would be randomized into 1A.2 or 1B.4 for their second round of participation) and participate in the study a second time. Enrollment will conclude once 160 subject-experiments have been completed for each study arm.

Inclusion Criteria

1. Age 18 years or older
2. Cirrhosis, as diagnosed by imaging, elastography, biopsy, or decompensation
3. Available email address
4. Arm 1: New patient visit for cirrhosis (and diagnosis within the last 6 months)
5. Arm 2: Previous cirrhosis diagnosis (>6 months)

Screening

For Arm 1, patients with a new diagnosis of cirrhosis will be identified by reviewing the University of Michigan Hepatology Clinic outpatient schedule and related notes in the Electronic Medical Record.

For Arm 2, Patients with >6 months history of cirrhosis diagnosis will be identified via Datadirect, previously established patient lists, and the University of Michigan Hepatology Clinic outpatient schedule.

Patients who meet the inclusion criteria will be randomized into one of the above subgroups and sent an email invitation to participate in the study. Potential participants will not be called or approached in person. The study invitation message will include contact information for study staff members in case these patients have any questions or would like to discuss the study in more detail before proceeding.

Procedures

The study will be conducted completely online, via REDCap. The initial study invitation email will include a link to the REDCap database, where participants will complete study questionnaires and activities. Informed consent for this study will be conducted online via REDCap.

Demographics Survey

Participants will be asked to report their age, sex, cause of cirrhosis, and any history of ascites, variceal bleeding, or HE.

Pre-Evaluation

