Based on their randomly assigned subgroup, participants will complete a Pre-Evaluation, consisting of 5-6 content-specific questions, to determine each participants' baseline level of content knowledge. Pre-Evaluation scores will be recorded, but not presented to participants.

Educational Intervention

Participants will be prompted to review the educational material associated with their assigned subgroup. This will involve reading a specific section of the Cirrhosis Toolkit or watching videos. Participants will be given unlimited time to review and interact with educational materials and will be prompted to complete the Post-Evaluation when ready.

Post-Evaluation

Participants will be directed to respond to a set of content-specific questions identical to the Pre-Evaluation they completed earlier in the study, but in a randomized order. Post-Evaluation scores will be presented to participants after they complete the optional feedback survey (below).

The change in score between pre-and-post-evaluations for each participant will inform the results of aims 1 and 2. For questions with multiple correct answers, no partial credit will be awarded.

Debrief

Participants will be informed that all mandatory study activity has been completed and thanked for their time.

The study debrief will present participants with multiple optional study activities:

- 1) Complete the Feedback Survey
- 2) Contact study staff for further questions
- 3) Review their Post-Evaluation Score and complete a brief survey response
- 4) Re-enroll in the study to 'learn more'

- 1) The Feedback Survey will consist of questions related to aims 3 and 4.

Questions:

- Did you find this material helpful? (Likert scale)
- Would you recommend this material to others? (yes/no)
- Would you prefer further educational materials in text or video format?
- Do you have any suggestions for improving these educational materials? (text box)

- 2) Participants will be given contact information for study staff members if they have any further questions.

3) Participants will have the option to review their post-evaluation scores only after all other activities have been completed, such as the feedback survey. Scores will be reported as [# correct]/[# of questions] Participants will be asked to reflect on their score:

-Are you satisfied with your score? (visual analog scale or Likert)

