-What are your next steps for further education? (select all that apply: Nothing, talk to Hepatologist, talk to Nurse, talk to nutritionist, talk to other medical professional, internet search, talk to family and friends, other (please explain))

4) Participants will be given the option to 'learn more' and re-enroll in the study. If participants elect to re-enroll, they will be randomized into a different subgroup of the same study arm.

Statistical Analysis

Aim 1: Matched pair Wilcoxon comparing pre-test and post-test scores in the whole study population.

Aim 2: Matched pair Wilcoxon comparing score change (from pre to post) between video group and text group.

Aim 3: Descriptive statistics of Likert scale results.

Aim 4: Will report key themes from patient open-ended responses.

Foreseeable Risks and Discomforts

The risks of this study are primarily psychological. Subjects may become frustrated if performing poorly on the pre-or-post-evaluations. Patients may have privacy concerns about study communication via email or conducting study activities online or on their personal device.

Expected Benefits

A potential direct benefit for participants is the opportunity to learn something new about cirrhosis.

Privacy and Confidentiality

Redcap, a secure and HIPAA-compliant electronic program, will be used for all data collection and study activities. Once randomized, participants will be identified only by a study ID number. Results of the testing and any other information provided by the subject are available for analysis under the heading of this number only, not by name or other personally identifiable information. No names or personally identifiable information will be collected or used in any publications.

We will keep a separate password protected screening log on the University shared drive in a secured location. Only study personnel will have access to the electronic screening log that maps the Subject ID number and Screening ID number (if applicable) to the participant's email address. Only limited identifiable data will be collected for screening purposes.

Data and Safety Monitoring

There are no safety concerns in this study. We will store data on a secure U-M server. Study staff will proofread data weekly to verify accuracy. PI will complete a comprehensive review of all data prior to analysis.

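### Age, HE history and ascites history are recorded before the material is shown, but the Aim 2 text-versus-video comparison does not adjust for them

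*Combined protocol and SAP*

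**What the plan says.** All references are to the combined protocol and SAP.

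- **Procedures, Demographics Survey:** "Participants will be asked to report their age, sex, cause of cirrhosis, and any history of ascites, variceal bleeding, or HE". This step is listed before the Pre-Evaluation and before the Educational Intervention, where "Participants will be prompted to review the educational material associated with their assigned subgroup". The answers are therefore pre-exposure baseline values.
- **Statistical Analysis:** one line per aim. The first aim gets a paired Wilcoxon on the two test scores with everyone pooled. The format comparison is given as "Aim 2: Matched pair Wilcoxon comparing score change (from pre to post) between video group and text group". The remaining two aims are handled by summaries of the ratings and by themes from open-ended answers. No line uses a demographic or history variable as a covariate, stratum, subgroup or balance table.
- **Overview, subgroup table:** four of the eight cells, such as "1A.2: Ascites Info", test ascites knowledge. Assignment to a topic does not depend on whether the patient has had ascites.
- **Overview, timing:** "before being invited to respond to the study survey, participants will be randomized into one of 4 subgroups per each study arm". Recruitment closes on completed records, 40 per subgroup, so a change score exists only for people who finish.

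**The concern.** Comparing text with video is the study's stated essential purpose, and the plan tests it without the baseline information that it collects. Two things could be lost.

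The first is precision. Living with ascites plausibly affects both what a patient knows about ascites and how much is left to learn. Age and HE plausibly affect how much is taken in. Variation explained by these variables can be removed from the error of the format comparison; an unadjusted test leaves it there.

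The second is balance in the data analysed. Format is randomised before invitation, but only finishers are scored. If people drop out after meeting a text section or a video, and do so differently by format and by age or HE history, the finishers in the two formats are no longer alike on those characteristics. Subtracting the Pre-Evaluation score does not fully deal with this, because these characteristics may affect the gain as well as the starting level.

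**Working it through.** **1. Counts.** 8 subgroups x 40 = 320, which matches 2 arms x 160 and the stated maximum. By format: 4 x 40 = 160 text and 160 video. By topic: 4 x 40 = 160 records test ascites knowledge. The plan gives no alpha, power, effect size or SD, so there is no power figure to reproduce.

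**2. Precision by formula.** Assumed: two-sided alpha 0.05, 80% power, independent records. The detectable difference is (1.960 + 0.842) x SD x sqrt(2/160) = 0.313 SD. If the covariates explain a share R2 of the variance of score change, multiply by sqrt(1 - R2). The unadjusted total needed to match is 320/(1 - R2). The documents do not give R2, so a range is shown.

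| R2 | Detectable difference (SD) | Power at 0.313 SD | Unadjusted total to match |
|---|---|---|---|
| 0 | 0.313 | 80% | 320 |
| 0.02 | 0.310 | 80.8% | 327 |
| 0.05 | 0.305 | 82.0% | 337 |
| 0.10 | 0.297 | 84.0% | 356 |
| 0.20 | 0.280 | 87.9% | 400 |

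**3. What the characteristics add beyond pre-score, by simulation.** Two sets of assumptions, each with 160 records per format.

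*Set A:* 1,500 trials per setting, 6-item test, format effect 0.35 log-odds, 40% ascites history, 30% HE history. The effect of HE on post-test performance is 0, 0.2, 0.4 or 0.8 log-odds; ascites and each SD of age have half that.

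| HE effect | Rank-sum on change | Post-score adjusted for pre-score | Plus ascites, HE, age | Added by the three |
|---|---|---|---|---|
| 0 | 53.7% | 78.0% | 77.8% | -0.2 |
| 0.2 | 47.8% | 72.9% | 73.3% | 0.4 |
| 0.4 | 52.1% | 74.3% | 77.1% | 2.8 |
| 0.8 | 48.3% | 67.8% | 78.7% | 10.9 |

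Most of the gain over the rank test comes from modelling the pre-score.

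*Set B:* 1,200 trials per setting, 5- and 6-item tests, 45% ascites history, 25% HE history, weak, moderate or strong effects. The comparator already adjusts for pre-score and topic. Adding age, HE and ascites-by-topic changed the SD of the format estimate, in percentage points, as follows:

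- weak: 2.44 to 2.40, and (2.44/2.40)^2 = 1.03; power 54 to 55%
- moderate: 2.66 to 2.52, and (2.66/2.52)^2 = 1.11; power 47 to 51%
- strong: 2.69 to 2.35, and (2.69/2.35)^2 = 1.31; power 42 to 51%

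These squared ratios are worth about 3%, 11% and 31% more records. Monte Carlo error on power is up to 1.5 points, so the weak case shows no clear gain.

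**4. Imbalance among finishers.** By formula, bias = difference in prevalence x effect of the factor. A 10-point difference in a factor worth 0.5 SD of change gives 0.10 x 0.5 = 0.05 SD. The standard error is sqrt(2/160) = 0.112 SD, so the shift is 0.05/0.112 = 0.45 standard errors and the false-positive rate is about 7%. A 20-point difference gives 0.10 SD and about 15%.

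By simulation in Set B, with no true format effect and video completion assumed to fall with age and HE (log-odds -0.6 each), the rates for weak, moderate and strong effects were:

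- Wilcoxon on change: 5.5, 6.8 and 8.8%
- regression including the characteristics: 5.7, 5.2 and 5.6%

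Monte Carlo error is about 0.6 points, so 5.5% cannot be told from 5%. In Set A, an imposed imbalance in ascites history alone, of 10 or 15 points, left the rank-sum test at 5.6 and 5.3%, which is no visible inflation.

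**The case against.** An unadjusted comparison of randomised groups is legitimate, and chance imbalance is already covered by the test's error rate. Each participant's own Pre-Evaluation score is subtracted, so prior knowledge does enter the outcome. Nothing in the documents says that older patients or those with HE finish videos less often, and time to review the material is unlimited. The simulated selection was built on age and HE and then removed by adjusting for age and HE, so the return to about 5% follows from the set-up. The precision gain may be nil, and pre-score is probably the stronger covariate. All of this stands. It limits the size of the point but does not answer it, because the values are already in hand and unused.

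Three stronger readings go too far.

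- A reader might infer that self-selection by email breaks the randomisation. Selection before the format is known does not unbalance the formats, and the documents do not say that the invitation reveals it. Only dropout that depends on format matters.
- A reader might infer false-positive rates of 11 to 16%. In Set B, 11.1 and 16.2% arose for a model with pre-score and topic only, under moderate and strong effects. That model is not in the plan. The figures bear only on the repair: a pre-score regression should not stop there.
- A reader might take assigning the ascites topic regardless of ascites history as a design flaw. Format is randomised within topic, so the format comparison is not harmed by it.

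**Conclusion.** The point holds in a modest form and is worth acting on. The omission is plain from the text: the baseline values come before exposure, and no analysis line uses them. The consequences are conditional.

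- **Precision:** the gain beyond pre-score adjustment runs from almost nothing to about 10 power points. It depends on how strongly age, HE history and ascites history predict learning, which the documents do not tell us.
- **Bias:** the false-positive rate of a Wilcoxon on change was about 5.5 to 9% under an assumed loss of video completers by age and HE. The documents do not establish that such a loss occurs.

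The simulations treat the records as independent, although a person may take part twice. Set B's effect sizes are known here only by their labels, so its figures indicate a range and do not predict this trial. The case for change rests on low cost and on fixing the covariates before results are seen, not on a demonstrated bias.

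**What to change.** In Statistical Analysis, Aim 2, replace the test; a Wilcoxon takes no covariates, so adding a sentence to the present line would not be enough. Pre-specify a regression of Post-Evaluation score (proportion correct, since tests have 5 or 6 items) on format, adjusted for:

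- Pre-Evaluation score, topic and study arm
- age and history of HE
- history of ascites, with an ascites-by-topic term

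Use standard errors clustered by participant, because re-enrolment lets one person contribute two records. Keep an unadjusted two-group rank comparison of score change as a sensitivity analysis. Tabulate age, HE history and ascites history by format among completers.

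No new data are needed. The model has eight coefficients (format, pre-score, topic, arm, age, HE, ascites, ascites-by-topic) plus an intercept, on 320 records. The price is those parameters and the move from a rank test to a regression on a short, bounded score. Adjustment corrects measured imbalance only; it does not replace a report of the numbers invited, started and completed in each subgroup.

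### Aim 3 is measured only in an optional survey offered after participants are told they have finished, so the preference result will rest on self-selected responders

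*Combined protocol and SAP*

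**What the plan says.** Specific Aims sets the objective of Aim 3: "Compare patients' preference for educational materials presented as text (Cirrhosis Toolkit) or video". Background and Significance also makes patient satisfaction part of the study's main purpose.

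The measurement is described under Debrief. The section opens: "Participants will be informed that all mandatory study activity has been completed and thanked for their time". It continues: "The study debrief will present participants with multiple optional study activities". The first of these activities is the survey: "The Feedback Survey will consist of questions related to aims 3 and 4". Two of its items bear directly on Aim 3: "Did you find this material helpful? (Likert scale" and "Would you prefer further educational materials in text or video format".

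The Post-Evaluation section, and item 3 of the Debrief, hold back the participant's score until the survey has been done. The Post-Evaluation section itself calls the survey optional.

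Statistical Analysis gives one line: "Aim 3: Descriptive statistics of Likert scale results". It states no denominator, no expected response rate, no comparison of responders with non-responders and no handling of non-response.

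**The concern.** A participant who stops at the thank-you message has done everything the protocol requires, counts as a completed subject-experiment, and contributes nothing to Aim 3. The trial can reach its recruitment target with an unknown fraction of the Aim 3 answers, and answers from people who have left cannot be recovered later.

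People who continue may differ from those who stop, for example in interest, in satisfaction, or in how they felt about the questions. If that difference is related to preference, the observed share choosing video is biased. If it is related to assigned format, the helpfulness ratings are compared between groups that randomization no longer keeps alike, and tabulating by assigned format does not repair this. At stake is one of four stated aims. Aims 1 and 2 use the mandatory evaluations and are not affected.

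**Working it through.** **1. Is Aim 3 measured anywhere else?**

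- Demographics Survey: age, sex, cause of cirrhosis and history of complications. Nothing on format.
- Pre-Evaluation and Post-Evaluation: knowledge questions only.
- Score reflection (Debrief, item 3): "Are you satisfied with your score? (visual analog scale or Likert". This is also optional, and it does not ask about format.
- Re-enrolment (Debrief, item 4): the second-round subgroup is randomized, not chosen, so it reveals no preference.

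The Feedback Survey is therefore the only source.

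**2. Planned numbers.** The Overview gives 8 subgroups of 40 subject-experiments: 8 × 40 = 320, and 4 × 40 = 160 per study arm. Both match the stated figures. Each format has four subgroups, so 4 × 40 = 160 per format. These targets count completed subject-experiments, and nothing ties them to a completed survey.

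**3. Outer limits under non-response.** The documents give no response rate and no expected preference share, so both inputs are assumptions. Let r be the proportion of completers who answer and p = 0.60 the share choosing video among those who answer. If every non-responder prefers text, the share among all completers is r × p. If every non-responder prefers video, it is r × p + (1 − r).

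| Response r | Answers out of 320 | Lower limit | Upper limit |
|---|---|---|---|
| 90% | 288 | 0.9 × 0.6 = 54% | 54% + 10% = 64% |
| 80% | 256 | 0.8 × 0.6 = 48% | 48% + 20% = 68% |
| 60% | 192 | 0.6 × 0.6 = 36% | 36% + 40% = 76% |

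The lower limit falls to 50% when r = 0.50 / 0.60 = 83%. Below that response, these limits no longer secure even the direction of preference.

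**4. A milder case.** Suppose true preference is 50/50, and 70% of those preferring video answer against 50% of those preferring text (assumed; 60% overall). The observed share for video is 0.70 / (0.70 + 0.50) = 58%. With equal response in both groups it would be 50%.

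**5. Sampling error for comparison** (95% half-width, p = 0.60, independent answers):

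- n = 320: 1.96 × √(0.24 / 320) = 0.054, or ±5.4 points.
- n = 160 (one format): 1.96 × √(0.24 / 160) = 0.076, or ±7.6 points.

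Participants may take part twice, so 320 subject-experiments may come from fewer than 320 people. The half-widths are then wider than shown.

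**The case against.** The plan has a mitigation of its own. Someone who has just been tested and wants the result must go through the survey first, which may lift response considerably. This stands, but only in part: the survey remains optional, and the incentive works on people who want their score, which is itself a form of selection.

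The size of the problem is assumed. A reader might take 36-76% as an estimate of the bias. It is not: it needs both a 60% response and non-responders who all hold the same preference. Nothing in the documents makes that more plausible than 90% response, where the limits are 54-64%. Nor do the documents show that response will be low, or that it will differ by assigned format. Foreseeable Risks and Discomforts mentions frustration after poor performance, which is a possible route to differential response but not evidence of it.

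Aim 3 is descriptive, with no test or decision rule, and an optional survey limits burden. That keeps the point minor, but a descriptive percentage is still distorted by selective response.

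A careless remedy could do harm: if the items were required on the Post-Evaluation form itself, someone unwilling to answer might leave before submitting, and Aim 1 and 2 data would be lost. This objection is sound and shapes the fix.

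**Conclusion.** The point holds as a low-cost improvement to one aim. As written, the plan yields a preference and helpfulness result from self-selected responders, with no stated denominator and no check on who is missing. How far, and in which direction, this moves the result cannot be determined from the documents; with nearly complete response it would be small. With an assumed 60% choosing video, non-response alone allows up to 6 points down or 4 up at 90% response (60% to 54% or 64%), and 24 down or 16 up at 60% response (60% to 36% or 76%). These are outer limits.

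A reader might infer that the preference result is already known to favour video, or that the text-versus-video comparison of knowledge is compromised. The documents support neither.

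A related gap is firm and needs no assumption: the text-or-video question is a two-way choice, and the Aim 3 analysis names only Likert results. The item that most directly answers the aim has no stated analysis.

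**What to change.** Place the helpfulness Likert item and the text-or-video preference item on a separate REDCap page, as part of the main study flow. The page should open after the Post-Evaluation has been submitted and saved, and before the Debrief completion message. Leave the recommendation item, the free-text suggestions, the score review and re-enrolment optional.

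In Statistical Analysis, extend Aim 3 to cover the two-way preference item. Report both items by assigned format, with the number answering out of all completers.

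The cost is a REDCap form edit, a short protocol change and two extra clicks per participant. Aim 1 and 2 data are protected because the Post-Evaluation is saved first. The change does not guarantee an answer from everyone, which is why the number answering must be shown. It also leaves selection from email-only recruitment (Screening) and from dropout before the Post-Evaluation is submitted.

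### Aim 2 names a matched-pair Wilcoxon for video against text, but individuals are randomised to format and no video/text pairs are defined

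*Combined protocol and SAP*

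**What the plan says.** All references are to the combined protocol and SAP.

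- **Purpose.** Background and Significance states: "Our essential purpose in this study is to compare the efficacy and patient satisfaction" of text and video education. Aim 2 carries the efficacy part. Aim 3, on preference, is analysed descriptively only.
- **Allocation.** Research Design and Methods, Overview: "participants will be randomized into one of 4 subgroups per each study arm, for a total of 8 possible subgroup assignments". Within an arm the four subgroups are two formats by two topics.
- **Second round.** Participation a second time is optional. In the Overview example, a person first assigned to 1A.1 (text, general information) is handled thus: "they would be randomized into 1A.2 or 1B.4 for their second round of participation". Both options are on the other topic. The Debrief section, option 4, is wider: "If participants elect to re-enroll, they will be randomized into a different subgroup of the same study arm".
- **Stopping recruitment.** "Recruitment for this study will conclude once 40 subject-experiments have been completed for each subgroup", so the count is of records and not of people.
- **Endpoint.** Under Post-Evaluation, each participant's change from pre to post serves Aims 1 and 2.
- **Tests.** Statistical Analysis gives "Aim 1: Matched pair Wilcoxon comparing pre-test and post-test scores in the whole study population" and then "Aim 2: Matched pair Wilcoxon comparing score change (from pre to post) between video group and text group".

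No section gives a matching variable, a matched set or a pairing rule for video and text participants. No section says how two records from one person are to be analysed.

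**The concern.** A matched-pair Wilcoxon (signed-rank) test works on one difference per pair, so here each pair must hold one video value and one text value. For Aim 1 the pairing is real, because each person has a pre and a post score. For Aim 2 that pairing has been used to form the change score, and what remains is two groups of differently randomised people.

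An analyst who follows the text has two ways out, both poor:

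1. **Pair video and text records arbitrarily.** A pairing fixed in advance would not inflate type I error. None is fixed, so the p-value rests on a choice that can be made after the data are seen.
2. **Use only people who took both formats.** They chose to re-enrol after seeing their first format, so a volunteer subset of unplanned size replaces the randomised comparison. Their two records always differ in round and, under the Overview example, always in topic as well.

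What is at stake is the only inferential comparison of text with video.

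**Working it through.** **1. The plan's own counts.** 8 subgroups × 40 = 320 records; 4 × 40 = 160 per arm; 4 text subgroups × 40 = 160 text records, and likewise 160 video. These reproduce. The documents give no alpha, power, effect size, SD or re-enrolment rate, so those below are assumptions.

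**2. How many natural pairs could there be?** Let *f* be the fraction of people who take a second round, with equal allocation.

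- People = 320/(1 + *f*); second rounds = *f* × people.
- Overview example: 1 of 2 options switches format, so pairs = 1/2 × second rounds.
- Debrief wording taken literally: 2 of the 3 other subgroups switch format, so pairs = 2/3 × second rounds.
- Share of records used = 2 × pairs/320.

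| *f* (assumed) | People | Second rounds | Pairs, Overview (share) | Pairs, Debrief (share) |
|---|---|---|---|---|
| 0 | 320 | 0 | 0 | 0 |
| 0.10 | 290.9 | 29.1 | 14.5 (9%) | 19.4 (12%) |
| 0.25 | 256 | 64 | 32 (20%) | 42.7 (27%) |
| 0.50 | 213.3 | 106.7 | 53.3 (33%) | 71.1 (44%) |
| 1.00 | 160 | 160 | 80 (50%) | 106.7 (67%) |

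Under the Debrief wording half of the pairs would be on the same topic: about 21, 36 or 53 at *f* = 0.25, 0.5 or 1. Even with universal re-enrolment, a third to a half of the records drop out.

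**3. What does arbitrary pairing do?** Simulation: rounded normal change scores, SD 1.3 items, 160 per format, 2,000 data sets, 100 random pairings each, two-sided 0.05.

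| True difference (items) | Rank-sum rejects | One pre-fixed pairing | Best of 10 | Best of 100 | Pairings on both sides of 0.05 |
|---|---|---|---|---|---|
| 0 | 5.0% | 5.0% | 8.6% | 11.6% | 9.8% |
| 0.275 | 43.6% | 43.8% | 54.3% | 60.9% | 30.8% |
| 0.4 | 74.6% | 74.8% | 82.2% | 86.3% | 24.1% |

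A pre-fixed pairing behaves like the rank-sum test. The last column shows the ambiguity itself and needs no selective reporting.

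**4. Does ignoring repeat participants matter?** In 6,000 null data sets per setting, with within-person correlation 0.3 or 0.5, a plain rank-sum test on all 320 records had type I error of 3.4–5.4%. The low end (3.4–3.9%) came with 100% re-enrolment under the Debrief wording. First-round records alone gave 4.7–5.4%.

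**5. What does a first-round-only analysis cost?** Detectable difference at 80% power, two-sided 0.05, with Wilcoxon efficiency 0.955: (1.960 + 0.842) × SD × √(2/n)/√0.955, where n is the number per format. First-round n is people/2. The first row treats all records as independent.

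| n per format | SD 1.0 | SD 1.3 | SD 1.6 |
|---|---|---|---|
| 160 (all records) | 0.32 | 0.42 | 0.51 |
| 128 (*f* = 0.25) | 0.36 | 0.47 | 0.57 |
| 106.7 (*f* = 0.5) | 0.39 | 0.51 | 0.63 |
| 80 (*f* = 1) | 0.45 | 0.59 | 0.73 |

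**The case against.** **It may be a slip of wording.** The Aim 2 line repeats the test name from the line above, and its object is a comparison of two groups. That is plausible, and the documents cannot settle it. But the text on file names a test that does not fit, and correcting the name alone would leave repeat participants without a rule.

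**The best-of-10 and best-of-100 rates are hypothetical.** This stands. They need an analyst to try many pairings and report the most favourable, and nothing in the protocol suggests that. The conclusion does not rest on them.

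**The Overview and Debrief can be read together.** The example may narrow the general rule to the other topic, and an invitation to learn more suggests new content. That reading is reasonable, and on it the smaller pair counts apply. One clarifying line would settle the matter.

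**The fix goes further than the defect.** In part this stands. The plain rank-sum test on all records was not materially inflated in the settings tried, and the protocol deliberately counts subject-experiments. Stratification and the mixed model are good practice rather than corrections. The minimum repair is an independent-groups test plus a stated rule for people with two records.

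**Conclusion.** The concern holds: the Aim 2 test is wrong as written. It cannot be computed on the randomised video and text groups without a pairing that the plan does not supply. This follows from the text alone and depends on no assumed figure.

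The size of the consequence does depend on assumptions. Restricting to natural pairs would use 20–50% of records at 25–100% re-enrolment under the Overview example, or 27–67% under the Debrief wording, and none if nobody re-enrols. Equal second-round allocation is also assumed, although recruitment is capped by subgroup. Arbitrary pairing leaves significance at 0.05 dependent on the pairing in roughly 10–31% of simulated data sets at SD 1.3.

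The test must be corrected before analysis, since it is the only planned test of text against video efficacy. The repeat-participant rule belongs in the same edit. Stratification and the clarification about topic are of lower priority.

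**What to change.** Replace the Aim 2 sentence with, for example:

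> Aim 2: Post-minus-pre change will be compared between participants randomised to video and to text, using first-round records only, by a Wilcoxon rank-sum test stratified by arm and topic (van Elteren), with an estimated difference and 95% CI. A supportive analysis will use all subject-experiments in a mixed model with format, arm, topic and round as fixed effects and a random participant effect.

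If the team prefers to keep all 320 records in the main analysis, make the mixed model, or an analysis with participant-clustered standard errors, the main one. Keep the matched-pair Wilcoxon for Aim 1's pre/post comparison. Reconcile the Overview and Debrief on whether a second round must be on the other topic.

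**Cost.** Two or three sentences of analysis wording, and no new data collection. The first-round-only choice loses precision because recruitment stops on records: at SD 1.3 the detectable difference rises from about 0.42 items to 0.47, 0.51 or 0.59 at 25%, 50% or 100% re-enrolment. The mixed model avoids discarding records but brings more modelling assumptions, on a score built from only 5–6 questions.
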